**Centering equity in FDA regulation: Front-of-package
food label effects in Latiné and limited English
proficiency populations**

NCT number NCT06293963

Document Date 07/26/2024

Study Protocol and Analytic Plan

Title: Centering equity in FDA regulation: Front-of-package food label effects in Latiné and limited English proficiency populations

NCT #: NCT06293963

Introduction

This study aims to determine the front-of-package label design that is most effective at helping Latiné consumers identify healthier products and to explore whether the benefits of front-of-package label design differ by English proficiency. This document pre-specifies our planned analytic approach prior to data collection.

Study Protocol

Participants will complete an online randomized experiment programmed in Qualtrics. After providing informed consent, participants will be randomly assigned to view 1 of 4 types of front-of-package nutrient labels: numerical label, interpretive text-only label, interpretive label containing a magnifying glass icon, or separated interpretive labels containing a magnifying glass icon. Participants will view 3 sets of similar products (with 3 products per set) displaying their assigned label type and will answer selection questions about the products. These selection questions will be repeated 3 times, once for each food product. The survey will also ask questions about reactions to the labels and demographics in the online survey.

Hypotheses

Correct identification of healthiest product (co-primary outcome): We predict that correct identification of the healthiest product will be highest for participants assigned to the separated interpretive magnifying glass icon label, followed by the interpretive magnifying glass icon label, the interpretive text-only label, and the numerical label (H1).

Correct identification of least healthy product (co-primary outcome): We predict that correct identification of the least healthy product will be highest for participants assigned to the separated interpretive magnifying glass icon label, followed by the interpretive magnifying glass icon label, the interpretive text-only label, and the numerical label (H2).

Correct identification of products high in nutrients (secondary outcome): We predict that correct identification of which products are high in nutrients of concern will be highest for participants assigned to the separated interpretive magnifying glass icon label, followed by the interpretive magnifying glass icon label, the interpretive text-only label, and the numerical label (H3).

Selection of healthiest product for purchase (secondary outcome): We predict selection of the healthiest product will be highest for participants assigned to the separated interpretive magnifying glass icon label, followed by the interpretive magnifying glass icon label, the interpretive text-only label, and the numerical label (H4).

Main Analyses

We will use a two-sided critical alpha of 0.05 to conduct all statistical tests. All confidence intervals presented will use a 95% confidence level. Analyses of the primary and secondary outcomes will include all participants according to the trial arm to which they were randomized.

For all of the selection tasks, participants will have a time limit to simulate real-world conditions where people make shopping decisions quickly. We will recode missing data as “no” or “incorrect” for all 4 selection outcomes. The healthiest product is defined as the one that is high in the fewest number of nutrients of concern (i.e., only 1 nutrient). The least healthy product is defined as the one that is high in the highest number of nutrients of concern (i.e., 3 nutrients). Correct identification of products high in nutrients is defined as identifying the products having 20% or more of the daily value of the nutrient or labeled with “high in,” per FDA’s guidance around “high” levels of nutrients of concern. The responses to these three correct identification tasks will be dichotomized as correct vs. incorrect. For the selection outcome, we will dichotomize the outcome to selection of the healthiest product vs. selection of either of the other two products.

We will descriptively report unadjusted means for the primary and secondary outcomes for each experimental arm. To test H1-H4, analyses will use mixed effects logistic regression models to examine the impact of label arm on the outcomes, accounting for repeated measures within participants. Models will regress the outcome on indicator variables for the labeling arm (excluding the numerical label as the referent) and indicator variables for product category, treating the intercept as random. Analyses will calculate average differential effects for each interpretative label compared to the numerical label, representing the differences in predicted probabilities by label type. We will also compare each interpretive label to each other. We will not adjust the p-value for each label type compared to the numerical label. We will adjust for multiple tests for the three additional pairwise comparisons (within each family of outcomes) among interpretive labels using a Bonferroni-Holm correction.

Exploratory Analyses

In exploratory analyses, we plan to report the impact of label type on the primary and secondary outcomes when stratifying by product type.

To examine whether the impacts of front-of-package label design on the co-primary outcomes differ by English proficiency, we will regress outcomes on label type, product type, English proficiency (high vs. limited), and the interaction between label type and English proficiency. These analyses will use linear probability models (rather than logistic regression) to aid in interpretation, as recommended for examining moderation for binary outcomes. We will use the same approach to determine whether the impacts of front-of-package label design differs by parental status.

Additionally, the survey will display 4 types of icon labels in random order, asking participants which label best signals when foods are high in sodium, saturated fat, and added sugars and which label most discourages purchasing of foods high in these nutrients. To assess which icon designs are most promising for front-of-package nutrition labels, we will calculate the proportion of participants who selected each label as best signaling when foods are high in sodium, saturated fat, and added sugars and the proportion who selected each label as most discouraging of purchasing foods high in these nutrients.

Sample Size and Power

We used G*Power 3 to estimate sample size needs. To be conservative, we powered the study to detect a difference in the co-primary outcomes between the 2 label designs that we anticipate will be most similar (i.e., the interpretative magnifying glass icon and interpretative text-only label). Power analyses assumed 55% of participants in the interpretative magnifying glass icon

condition would correctly identify the least healthy and healthiest products (based on a prior study using similar methods) and a two-tailed critical alpha of 0.017 (0.05 divided by 3 to correct for multiple comparisons). Under these assumptions, a sample of 1,000 per condition (4,000 total) yields 80% power to detect effects of $OR=1.16$ or larger between any 2 label designs for each primary outcome. This is a conservative estimate of effect size based on prior studies showing effect sizes of 1.10–1.80 between similar labels. This would be considered a small effect size, equivalent to Cohen's $d=0.08$.

Interim Analysis

No interim analyses are planned.

Exclusions and Outliers

We will exclude participants who complete the survey implausibly quickly (defined as <1/3 of the median completion time). We will exclude participants who complete less than 90% of the survey.

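### Adding English proficiency to the H1–H2 models is an optional, low-cost gain in precision, small at best, and nil if proficiency does not predict accuracy

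*Combined protocol and SAP*

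**What the plan says.** The combined protocol and SAP specifies mixed effects logistic regression for H1–H4 under Main Analyses. The fixed part is: "Models will regress the outcome on indicator variables for the labeling arm (excluding the numerical label as the referent) and indicator variables for product category". The intercept is random, and no participant characteristic is included. Results are to be reported as differences in predicted probability between labels. On multiplicity: "We will not adjust the p-value for each label type compared to the numerical label". The three comparisons among interpretive labels get a Bonferroni-Holm correction. On who is analysed, the primary and secondary analyses will "include all participants according to the trial arm to which they were randomized". Exclusions and Outliers then removes very fast responders and those who complete less than 90% of the survey.

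The Introduction gives as a second aim to "explore whether the benefits of front-of-package label design differ by English proficiency". Exploratory Analyses follows this up by asking whether the "impacts of front-of-package label design on the co-primary outcomes differ by English proficiency". It uses a linear probability model with label type, product type, proficiency (high or limited) and the label-by-proficiency interaction. Parental status is treated alike: "We will use the same approach to determine whether the impacts of front-of-package label design differs by parental status".

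On when these characteristics are collected, Study Protocol says only: "The survey will also ask questions about reactions to the labels and demographics in the online survey".

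**The concern.** Proficiency will be collected, its two categories are already fixed, and it is already to be regressed on the co-primary outcomes. It is nonetheless left out of the models that test H1 and H2, and no reason is given. The tasks involve reading labels under a time limit, so it is plausible, though nowhere stated, that people with limited proficiency answer correctly less often. If so, part of the between-person variation in accuracy is explainable, and removing it would narrow the label contrasts without more participants.

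What is at stake is precision only. The trial is sized for a small difference between its two most similar labels (OR 1.16), so a small gain has some value. A covariate is also most credible when it is named before data collection.

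**Working it through.** **The plan's own figure.** Sample Size and Power states 80% power for OR 1.16 with 1,000 per arm, 55% correct and two-tailed alpha 0.017. From 55%, OR 1.16 leads to 58.6% upward or 51.3% downward, a difference of about 3.7 points either way. A two-proportion calculation gives 23% power with one answer per person. With three answers per person it gives about 68% if they are independent, and about 35% at a within-person correlation (ICC) of 0.5. The 80% was not reproduced. That is a separate matter: the point here does not rest on it, and adjustment does not cure it.

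**Inputs from the documents.** 55% correct, three answers per participant, 1,000 per arm and 4,000 in total, OR 1.16, alpha 0.017 in the power calculation and 0.05 for tests.

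**Inputs assumed, because the documents give none.** Share with limited proficiency s = 30–50%, ICC = 0.2–0.5, accuracy gap between proficiency groups d = 5–20 points.

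**Step 1: variance of a participant's mean of three answers.**
V = 0.55 × 0.45 × (1 + 2·ICC) / 3, which gives
- ICC 0.2: 0.1155
- ICC 0.35: 0.14025
- ICC 0.5: 0.165

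**Step 2: share of V explained by proficiency.** r = s(1 − s)d² / V. The variance of a label contrast falls by this share, and 4,000 × r is the number of participants the adjusted analysis could do without.

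| Gap d | Low end (s = 0.3, ICC 0.5) | High end (s = 0.5, ICC 0.2) |
|---|---|---|
| 0 | 0 | 0 |
| 5 points | 0.21 × 0.0025 / 0.165 = 0.32% (13) | 0.25 × 0.0025 / 0.1155 = 0.54% (22) |
| 10 points | 0.21 × 0.01 / 0.165 = 1.27% (51) | 0.25 × 0.01 / 0.1155 = 2.16% (87) |
| 20 points | 0.21 × 0.04 / 0.165 = 5.09% (204) | 0.25 × 0.04 / 0.1155 = 8.66% (346) |

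At the midpoints (s = 0.4, d = 12.5 points, ICC 0.35): 0.24 × 0.015625 / 0.14025 = 2.67%, or 107 participants.

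**Step 3: interval width at the midpoints.** Half-width = 1.96 × √(2V(1 − r)/1000).
- Unadjusted: 1.96 × √(2 × 0.14025/1000) = 3.283 points.
- Adjusted: 3.283 × √(1 − 0.0267) = 3.238 points.

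**Step 4: power for 55.0% versus 51.3%, same variance in both arms.**
- Midpoints, alpha 0.017 (strictest Holm step, among interpretive labels): 42.8% to 44.0%.
- Midpoints, alpha 0.05 (each label against numerical, unadjusted p-value): 59.7% to 60.9%.
- Range at alpha 0.017: from 36.2% to 36.3% in the least favourable setting (s = 0.3, gap 5, ICC 0.5), and from 51.7% to 56.2% in the most favourable (s = 0.5, gap 20, ICC 0.2).

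Allowing unequal variances lowers the midpoint power values by about 0.2 points and leaves the gain of about 1.2 points unchanged.

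**Simulation checks.** With linear adjustment of participant means at the midpoints, 30,000 replicates gave a variance reduction of 2.60% and half-widths of 3.28 and 3.24 points. With no gap, 15,000 replicates gave a change of −0.07%, so no material loss. The planned random-intercept logistic model was also simulated, with only 6 replicates per setting. The ratio of adjusted to unadjusted standard error was 1.000 with no proficiency effect, 0.985 at a gap of about 11 points and 0.945 at about 22 points. The gain is therefore not an artefact of the linear approximation.

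**The case against.** The strongest reply is that nothing is wrong with the plan. A pre-specified model without participant covariates is a legitimate choice in a randomized comparison of about 4,000 people. The benefit rests wholly on assumed inputs. The 12.5-point midpoint is only the centre of a chosen range, and the top of that range, a 20-point gap, has no support in the documents. At the midpoint the half-width shrinks by about 0.04 points, which would rarely change a conclusion. Planned use as an effect modifier is not evidence that proficiency predicts accuracy, and precision depends on prognostic strength, not on being named in an aim. Timing is unstated, so the change may not be usable. Adding the term for H1–H2 alone would also give the co-primary and secondary outcomes different models.

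Most of this stands, and it limits the point to an optional improvement. It does not remove it. With no accuracy gap, one extra term costs almost nothing in a sample of this size. A brief label exposure is unlikely to change a person's English proficiency, so the timing condition can probably be met, although the authors must confirm it. The different-models objection is met by extending the term to H3–H4 if the authors prefer one common model; no gain is claimed there.

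**Conclusion.** The point holds as an optional improvement. The H1–H2 models omit a participant characteristic that the trial already plans to relate to the same outcomes. Including it would narrow the label contrasts slightly if it predicts accuracy, and would do nothing otherwise. The reduction in variance is zero with no gap, about 0.3–2.2% for gaps of 5–10 points, and at most 8.7% at 20 points. These figures assume 30–50% limited proficiency and ICC 0.2–0.5. The unadjusted contrasts remain valid and unbiased, and the gain does not restore the stated 80% power. Confidence is medium, because the prognostic strength of proficiency and the timing of its measurement are not in the documents.

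**What to change.** 1. State when in the survey English proficiency is asked.
2. If it is asked before label exposure, or can be justified as a stable trait that exposure cannot affect, pre-specify it (high or limited) as a fixed main effect in the H1–H2 mixed logistic models. Add a category for missing proficiency, so that nobody otherwise in the analysis set is dropped because of this variable.
3. Keep the current effect measure: report label differences in predicted probability, averaged over the observed proficiency mix and the random-intercept distribution.
4. Keep the unadjusted model as a sensitivity analysis.
5. If the condition in step 2 cannot be met, leave the unadjusted model as primary.

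Extending the term to H3–H4 is optional. Parental status has the same exploratory role, but proficiency is the one proposed because it is named in the study aim and bears directly on reading labels.

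The cost is one model term, a missing-data rule for it, an averaging step, one sensitivity model for each co-primary outcome and a sentence on timing. No new data or extra participants are needed.

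### Must the three comparisons with the numerical label be adjusted for multiplicity, and must the plan say how the two co-primary outcomes combine?

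*Combined protocol and SAP*

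**What the plan says.** All places are in the combined protocol and SAP.

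- **Main Analyses** sets one level for everything: "We will use a two-sided critical alpha of 0.05 to conduct all statistical tests". The numerical label is the reference arm: "Models will regress the outcome on indicator variables for the labeling arm (excluding the numerical label as the referent". With four arms this gives three comparisons per outcome, and for these the text is explicit: "We will not adjust the p-value for each label type compared to the numerical label". The other three pairs are handled differently: "We will adjust for multiple tests for the three additional pairwise comparisons (within each family of outcomes) among interpretive labels using a Bonferroni-Holm correction".
- **Hypotheses** names two co-primary outcomes: H1 (healthiest product) and H2 ("Correct identification of least healthy product (co-primary outcome"). Each has its own predicted ordering of the four labels. Nothing says whether a claim needs both outcomes or only one.
- **Sample Size and Power** uses a "two-tailed critical alpha of 0.017 (0.05 divided by 3 to correct for multiple comparisons") and states 80% power for an odds ratio of 1.16 "or larger between any 2 label designs for each primary outcome".
- **Introduction** gives the aim: "This study aims to determine the front-of-package label design that is most effective".

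**The concern.** Three things look wrong on a first reading.

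1. The comparisons listed first, which would support a statement that an interpretive label beats the numerical one, have less protection than the comparisons described as additional.
2. Two outcomes are called co-primary with no joint rule, alpha split or hierarchy. A sponsor could in principle announce success on whichever outcome came out significant, and six unadjusted tests would then feed one claim.
3. The power section applies a third of 0.05 to any pair of labels, whereas the analysis applies the full 0.05 to half of the pairs.

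At stake is the credibility of a finding meant to inform food-label regulation. If the chance of a spurious win were really one in four or five, that would matter.

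**Working it through.** **The plan's own figure.** No familywise error rate is stated, so there is none to reproduce. The only design figure is 80% power at two-sided 0.017 with 1,000 per arm, 55% correct and an odds ratio of 1.16. Treating three responses per person as 3,000 independent observations per arm, a two-proportion calculation gives about 68%. The equivalent d = ln(1.16)·√3/π = 0.082 gives 78%. The documents do not name the G*Power procedure or the within-person correlation, so the match is approximate. The error rates below do not depend on it.

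**Error rate for one outcome.** Inputs: three two-sided tests at 0.05 (critical value 1.96), four equal arms and a shared reference. Two contrasts sharing a reference arm of equal size correlate at 0.5. Then

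P(at least one rejection) = 1 − P(|Z1|, |Z2|, |Z3| all ≤ 1.96) = 12.5%.

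Treating the tests as independent would give 1 − 0.95³ = 14.3%, which is too high. Counting only rejections that favour an interpretive label gives 6.3%.

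**Error rate if either outcome counts.** This needs a between-outcome correlation r, which the documents do not give. Simulation with 1,000,000 draws or more per value gives:

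| r (assumed) | Any false rejection | Favouring an interpretive label |
|---|---|---|
| 0 | 23.5% | 12% |
| 0.5 | 22% | 11% |
| 0.7 | 20% | 10% |
| 0.9 | 17% | 9% |
| 1 | 12.5% | 6.3% |

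Both outcomes come from the same person viewing the same labelled products, and unanswered items are scored incorrect on both. Zero correlation is therefore an unlikely extreme.

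**Which row applies?** The plan has two hypotheses, each tied to one outcome. Power is stated for each primary outcome. The planning alpha is 0.05 divided by 3, not by 6, which fits a family of three comparisons within one outcome. All of this points to inference outcome by outcome, for which the figure is 12.5% (6.3% in the favourable direction). The table describes a pooled claim that the plan nowhere makes.

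**The aim of finding the most effective label.** Suppose this means beating every other label, a reading the plan does not spell out. An interpretive label must then win its two Holm-adjusted contrasts as well as its unadjusted one.

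- With all labels equal, a simulation for one outcome gives a false interpretive winner in 0.2% of runs.
- If one interpretive label merely ties the numerical label and both stand far above the rest, one test in one direction remains: 0.05/2 = 2.5%.
- If all three interpretive labels truly beat the numerical one, the Holm contrasts govern, and they are held at 5%.

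The unadjusted contrasts do not inflate this claim.

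**What adjustment would buy and cost.** Holm over the three numerical contrasts lowers the one-outcome rate from 12.5% to about 4.5%. For the cost, take 1,000 per arm, 3 items, a design effect of 1 + 2·ICC, and 55% against a lower rate p₂. With ICC 0.3 (assumed), the effective n is 3,000/1.6 = 1,875 per arm and

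z = (0.55 − p₂)/√{[0.55·0.45 + p₂(1 − p₂)]/1,875}.

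- Odds ratio 1.16 (p₂ = 0.513): z = 2.27. Power is Φ(2.27 − 1.96) = 62% at 0.05 and Φ(2.27 − 2.39) = 45% at 0.0167.
- 5 points (p₂ = 0.50): z = 3.07. Power is 87% and 75%. At ICC 0.1 it is 94% and 88%; at ICC 0.5, 78% and 64%.
- 7 points (p₂ = 0.48): z = 4.30. Power is 99% and 97%.

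These use Holm's strictest step. The loss is smaller for a label tested after others have been rejected.

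Adding a rule that a label must win on both outcomes lowers power further. At 0.0167 with independent outcomes, joint power is 0.45² = 20% for the odds ratio of 1.16 and 0.75² = 56% for 5 points.

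**The case for a change.** The best case for a change is that disclosure does not control error. H1 and H2 rank all four labels, so the six pairs per outcome serve one question, and the plan gives no reason to protect three pairs and not the others. Holm is already in the plan, its strictest step equals the planning alpha, and adopting it needs no extra participants. A both-outcomes rule alone would not settle the matter either. If every label helped on one outcome and none on the other, unadjusted tests would still wrongly credit an interpretive label 6.3% of the time, against 2.2% with Holm.

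Part of this stands. The arithmetic is right, the documents contain no sentence joining H1 and H2, and a statistician who preferred Holm throughout would be on firm ground.

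It does not establish a defect. The two sets differ in kind: one is a small set of planned contrasts against a single reference, each answering its own question, and the other compares every pair of the remaining labels. Leaving the first set unadjusted with disclosure is a recognised position. The planning alpha matches the comparison the study was powered on, icon against text-only, which is in the Holm family. Applying it to any pair is conservative for power and contradicts nothing. The both-outcomes rule would replace two separate hypotheses with a joint claim the plan does not make.

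**Conclusion.** No change to the plan follows. The unadjusted contrasts are a deliberate, pre-specified and visible choice, and no stated error rate is breached. Their cost, if all four labels are equal, is a 12.5% chance of at least one false rejection per outcome, half of it (6.3%) in the direction that would credit an interpretive label. The 20–24% figure needs two further conditions: that a win on either outcome counts, and that the outcomes correlate between 0 and 0.7. The first is not the natural reading of the plan, and the second is an assumption.

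The missing sentence on how H1 and H2 relate is a gap that analysts can fill sensibly by reporting each outcome on its own and repeating that the numerical-label p-values are unadjusted. Readers who want stricter control can apply Holm to the three reported p-values themselves. Making it mandatory is a trade-off: about 8 percentage points less familywise error per outcome (12.5% to 4.5%), for up to 17 points of power at the odds ratio of 1.16 (62% to 45%) and 12 points at a 5-point difference (87% to 75%), both at an assumed within-person correlation of 0.3.

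### Holm is valid for the three comparisons among interpretive labels but stricter than needed at its second step; a restricted step-down gains some power under the same 5% ceiling

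*Combined protocol and SAP*

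**What the plan says.** Main Analyses sets the general level: "We will use a two-sided critical alpha of 0.05 to conduct all statistical tests". For the comparisons with the reference arm it adds: "We will not adjust the p-value for each label type compared to the numerical label". It then says "We will also compare each interpretive label to each other", and adjusts these "three additional pairwise comparisons (within each family of outcomes) among interpretive labels using a Bonferroni-Holm correction". The adjusted family is therefore all pairs of exactly three labels (text-only, icon, separated icon), with Holm thresholds 0.05/3, 0.05/2 and 0.05. The plan specifies no omnibus or closed test.

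Sample Size and Power bases the study on icon versus text-only, the pair expected to be most alike, at a "two-tailed critical alpha of 0.017 (0.05 divided by 3 to correct for multiple comparisons". It assumes 55% correct in the icon arm and states 80% power for an odds ratio of 1.16 with 1,000 per arm.

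**The concern.** Holm's second threshold of 0.025 allows for two null hypotheses still being true after the first rejection. Among all pairs of three groups that cannot happen. Equality is transitive, so if two of the three pairs are equal, the third is equal too. Once one pair is known to differ, at most one true null remains, and no further division of alpha is needed.

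The label-versus-label contrasts bear on the study's stated aim of finding the most effective design, and one of them sets the sample size. A threshold stricter than necessary costs power on those contrasts. The question is how much.

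**Working it through.** **Inputs.** From the plan: alpha 0.05 two-sided; three interpretive arms of 1,000; 55% in the icon arm; odds ratio 1.16; three answers per person for each outcome (Study Protocol); hypothesised order text-only < icon < separated icon (Hypotheses). Assumed, because the documents do not give it: the within-person intraclass correlation (ICC), taken from 0 to 0.5.

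**The plan's own figures.** 0.05/3 = 0.0167, which matches the stated 0.017. The 80% does not reproduce. Odds ratio 1.16 below 55% is 51.3%. With one answer per person, SE = √[(0.55×0.45 + 0.513×0.487)/1000] = 0.0223, so the standardised difference is 0.0369/0.0223 = 1.66 and power at 0.017 is 23%. Three answers per person multiply 1.66 by √[3/(1+2·ICC)], giving power of 68% at ICC 0, 45% at 0.3 and 36% at 0.5. That is a separate issue. It matters here only because it affects which rows below are realistic.

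**Validity of the restricted procedure.** Rule: reject a pair if the smallest p-value is ≤ 0.05/3 and the pair's own p-value is ≤ 0.05.
- All three labels equal: a false rejection requires the smallest p-value ≤ 0.05/3, so by Bonferroni the error is ≤ 5%.
- Exactly one pair equal: the only true null must have p ≤ 0.05, so the error is ≤ 5%.
- No pair equal: there is no true null.

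The argument needs the three nulls to be equalities of arm parameters from one model, which the planned regression on arm indicators provides.

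**Where the methods differ.** They differ only when p(1) ≤ 0.05/3 and 0.025 < p(2) ≤ 0.05. Holm then stops after one rejection; the restricted rule continues. In every other case the decisions are identical, so no Holm rejection can be lost. The first step is shared, so the chance of at least one rejection is the same.

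**Size of the gain.** Simulation of three independent arm estimates with equal SE (normal approximation, 2,000,000 draws), with the SE of a difference set to 1.

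Equal steps in the hypothesised order, icon versus text-only:

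| Setting | Step | Gain (points) |
|---|---|---|
| Plan's target: 80% at 0.017 | 2.387 + 0.842 = 3.23 | 0.2 |
| OR 1.16, three answers, ICC 0 | 1.66×√3 = 2.87 | 1.0 |
| OR 1.16, ICC 0.1 | 1.66×√2.5 = 2.62 | about 2 |
| OR 1.16, ICC 0.3 | 1.66×√1.875 = 2.27 | about 5 |
| OR 1.16, ICC 0.5 | 1.66×√1.5 = 2.03 | about 7 |

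Power goes from 89.5% (Holm) to 89.7% (restricted) at the target effect, from 80.7% to 81.8% at ICC 0, and from 57.0% to 61.9% at ICC 0.3.

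Icon = separated icon, both better than text-only:

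| Setting | Per true difference | Both true differences found | Family-wise error |
|---|---|---|---|
| Plan's target | 82.6% → 86.2% | 74.1% → 81.2% | 3.7% → 5.0% |
| OR 1.16, ICC 0 | 71.4% → 75.8% | 59.8% → 68.6% | 3.3% → 4.9% |
| OR 1.16, ICC 0.3 | 47.8% → 52.2% | 34.0% → 42.8% | 2.7% → 4.6% |
| OR 1.16, one answer | 24.6% → 27.4% | 13.8% → 19.3% | 2.3% → 3.8% |

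With all three labels equal, family-wise error is 4.4% under both. No draw in any setting had a Holm rejection that the restricted rule missed.

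**The case against.** The strongest case for leaving the plan alone is that Holm is standard, pre-specified and controls family-wise error at 5%. Nothing in the document is contradicted or invalid because of it. That stands. A reader might infer that the plan contains an error, and the documents do not support that.

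A reader might also infer that Holm's strictness buys nothing at all. That goes too far. When two labels are truly equal, the restricted rule makes realised false positives more frequent, as the second table shows. The guaranteed ceiling is the same, however: with one label far from two equal ones, Holm's own error also reaches 5.0%. The lower realised figure elsewhere is unused alpha, not a promise, but giving it up is a choice that the sponsor should make knowingly.

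A third tempting reading is that the power cost is large. At the plan's target effect with equal steps it is 0.2 points. The larger gains arise when real power is well below 80% or when two labels tie. The change does not repair low power: at ICC 0.3 with equal steps, icon versus text-only still reaches only about 62%.

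Finally, the plan's phrase about families of outcomes could mean three tests per outcome or six tests pooled over the two co-primary outcomes. The 0.05/3 in Sample Size and Power favours three per outcome, but the text does not settle it. If six tests were meant, the per-outcome rule would loosen control: with all labels equal and independent outcomes, the chance of any false rejection is 1 − (1 − 0.044)² = 8.6%. This objection stands, and the fix must deal with it.

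**Conclusion.** The point holds as one of efficiency. Holm is valid but needlessly conservative at its second step for all pairs of three labels. The restricted step-down keeps every Holm rejection and adds some, with the same guaranteed 5% family-wise error per outcome and an unchanged chance of at least one rejection. The gain ranges from negligible at the plan's target effect with equal steps to about 7 points at ICC 0.5, with about 3 to 5 points per true difference when two labels tie.

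The logical argument assumes no effect size or correlation. The sizes rest on the normal approximation, equal standard errors, the assumed ICC range and the configurations shown. The 5% statement rests on reading the family as three tests within one outcome. This is an optional improvement; leaving Holm in place would be defensible.

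**What to change.** In Main Analyses, replace the Holm sentence with:

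> Within each outcome (three tests per outcome, consistent with the 0.05/3 in the power section), the three comparisons among interpretive labels use Shaffer's logically restricted step-down: the smallest p-value is tested at 0.05/3; if it is rejected, each of the other two is tested at 0.05. Adjusted p-values are min(1, 3p(1)) for the smallest and min(1, max(3p(1), p)) for the others.

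State explicitly that this interprets the family of outcomes as a single outcome. If the sponsor meant to pool the co-primary outcomes, the family and its thresholds must be set for that instead, and the power section brought into line.

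The cost is one sentence, before data collection as the Introduction intends. It needs no new data, model or software and leaves the 0.017 in the power section unchanged. The trade to accept is a higher realised family-wise error within the 5% ceiling. The property is special to three groups, so the rule should not be extended unchanged to all six pairs of the four arms.
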